8.1 Primary

The primary objectives of the study are to describe receipt of the educational materials and knowledge about the patient/caregiver educational materials, among patients with Ph– R/R B-precursor ALL receiving Blincyto and their caregivers.

8.2 Secondary

The secondary objectives of the study are:

- To describe behaviours outlined in the patient/caregiver educational materials, among patients with Ph– R/R B-precursor ALL receiving Blincyto and their caregivers.
- To describe the level of understanding of key safety messages in the patient/caregiver educational materials, among patients with Ph– R/R B-precursor ALL receiving Blincyto and their caregivers.
- To describe usage of the educational materials, among patients with Ph– R/R B-precursor ALL receiving Blincyto and their caregivers.

This study will help indicate if the aRMMs are successful if a majority of patients and caregivers participating in the survey confirm receipt of the patient/caregiver brochure and card and have knowledge of key safety messages in the patient/caregiver brochure. These results will be interpreted in context of the wider study including the secondary objectives and the results of individual questions, response rate and recruitment. In addition, any available information external to the study to help understand the experience of the patient aRMMs will be considered to determine what action, if any, should be taken.

9. Research Methods

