As a requirement linked to the Blincyto Risk Management Plan (RMP), Amgen as the Marketing Authorisation Holder (MAH), shall ensure that in each member state where Blincyto is marketed all healthcare professionals (HCPs) who are expected to prescribe, dispense or administer the product, and patients/caregivers who are expected to use the product, be provided with the aRMMs presented in Table 1.

Table 1. Blincyto aRMMs in the European Union

Measure	Target population	Key messages
Educational brochure for nurses	Haematology Nurses	
 Remarks on the importance of reporting adverse drug reactions (ADRs) Description of the administration procedures of Blincyto Description on patient's monitoring and management of early signs and symptoms of neurological events Recommendation for patients not to drive while receiving Blincyto and to contact immediately the treating physician / nurse if they experience neurological symptoms
Educational brochure for physicians	Haematologist Oncologist	
 Remarks on the importance of reporting ADRs Information on treatment with Blincyto, administration and posology, duration of hospitalisation, interruption and/or permanent discontinuation of the treatment
Educational brochure for pharmacists	Hospital Pharmacists	
 Remarks on the importance of reporting ADRs Detailed description of the reconstitution and preparation procedures of Blincyto infusion solution for intravenous administration, using aseptic techniques
Educational brochure for patients/caregivers	ALL patients receiving Blincyto and their caregivers	
 Remarks on the importance of reporting ADRs Description of the administration procedures of Blincyto and how to reduce the risk of MEs while using the infusion pump. Description of the main signs and / or symptoms of neurologic events and the importance of notifying the treating physician or nurse immediately if symptoms occur Recommendation for patients not to drive while receiving Blincyto
Patient Card	ALL patients receiving Blincyto and their caregivers	
 Remarks on the importance of reporting ADRs A warning message for HCPs treating the patient at any time, including emergency conditions, that the patient is using Blincyto Contact details of the Blincyto prescriber Blincyto treatment start date

Effectiveness of Blincyto educational tools

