7.3 Statistical Inference (Estimation or Hypothesis[es])

This study is descriptive and therefore no formal hypothesis will be tested.

8. Research Question and Objectives

This survey aims to address the following research questions:

- Has key safety information contained in the patient/caregiver educational materials reached the target population?
- What is the level of knowledge and understanding of the target audience with regard to the key safety information described in the patient/caregiver educational materials?
- What is the level of the behaviours outlined in the educational materials?
- Are the patient/caregiver educational materials used as intended?

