9.7.2.4 Analysis of the Primary and Secondary Endpoint(s)

The primary analysis for the survey will be performed for patients and caregivers separately for the endpoints below described, and will include the total number of patients and caregivers with valid responses to all relevant questions and the percentage of patients and caregivers with a positive response for the endpoint:

- **Receipt** will be assessed through the percentage of patients and caregivers who received the brochure and/or card.
- A mean **knowledge** score will be created to summarise individual patient and caregiver scores. An individual patient/caregiver score is calculated as the proportion of all knowledge questions with correct responses.

The secondary analyses are:

- A mean **behaviour** score will be created to summarise individual patient and caregiver scores. An individual patient/caregiver score is calculated as the proportion of all behaviour questions with correct responses.
- Among patient and caregivers who have read the patient/caregiver brochure and/or card, an ordinal scale will describe the self-reported level of **understanding**.
- A mean **usage** score will be created to summarise individual patient and caregiver scores. An individual patient/caregiver score is calculated as the sum of the 'value' of responses to all usage questions (ordinal scale) divided by the maximum possible

score. Among patients and caregivers who have not read the materials, a categorical variable will describe the reasons for not reading them.

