5.1	Does the protocol describe how the study exposure is defined and measured? (e.g. operational details for defining and categorising exposure, measurement of dose and duration of drug exposure)				
5.2	Does the protocol address the validity of the exposure measurement? (e.g. precision, accuracy, use of validation sub-study)				
5.3	Is exposure classified according to time windows? (e.g. current user, former user, non-use)				
5.4	Is exposure classified based on biological mechanism of action and taking into account the pharmacokinetics and pharmacodynamics of the drug?				

Comments:

No exposure-outcome association will be assessed

Section 6: Outcome definition and measurement		Yes	No	N/A	Section Number
6.1	Does the protocol specify the primary and secondary (if applicable) outcome(s) to be investigated?				4, 9.3
6.2	Does the protocol describe how the outcomes are defined and measured?				4, 9.3
6.3	Does the protocol address the validity of outcome measurement? (e.g. precision, accuracy, sensitivity, specificity, positive predictive value, prospective or retrospective ascertainment, use of validation sub-study)				4, 9.3
6.4	Does the protocol describe specific endpoints relevant for Health Technology Assessment? (e.g. HRQoL, QALYs, DALYs, health care services utilisation, burden of disease, disease management)				

Comments:

This is a cross-sectional survey with no HEOR objectives

Section 7: Bias		Yes	No	N/A	Section Number
7.1	Does the protocol describe how confounding will be addressed in the study?				

ENCePP Checklist for Study Protocols (Revision 3)

Section 7: Bias	Yes	No	N/A	Section Number

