Appendix F. Educational materials

Bincyto Patient Card

Version 1.0

BLINCYTO® (blinatumomab) Approved: September –2015

Educational Brochure for Patients and Caregivers

Patient Card

Please show this card to all emergency and healthcare providers

Information about BLINCYTO® ▼ (blinatumomab)

My name is _____

I am being treated with BLINCYTO a treatment for relapsed/refractory acute lymphoblastic leukemia, which can lower my immune system.

I started treatment on _____

Before providing any treatment, please call my prescribing physician at the number below. If any medical evaluations are undertaken, please provide copies of all medical records, including any treatments and/or test results, to the doctor(s) named below.

	Name	Hospital	City	Phone Number
Haematologist				
Oncologist				
Haematology Nurse				

▼ This medicine is subject to additional monitoring. This will allow quick identification of new safety information. You can help by reporting any side effects you may get to <##>. By reporting side effects, you can help provide more information on the safety of this medicine.

Bincyto Educational Brochure for Patients and Caregivers

Version 1.0

BLINCYTO[®] ▼ (blinatumomab) Approved: September-2015

Educational Brochure for Patients and Caregivers

BLINCYTO[®] ▼ (blinatumomab)

Important Risk Minimisation Information for Patients and Caregivers

This educational brochure contains important information you should know before receiving BLINCYTO.

This educational material is essential to ensure the safe and effective use of the drug and appropriate management of the important selected risks. Please read it carefully before taking the medicinal product.

If you have any questions about BLINCYTO please speak to your doctors or nurses, or refer to the Patient Leaflet, provided with this brochure.

▼ This medicine is subject to additional monitoring. This will allow quick identification of new safety information. You can help by reporting any side effects you may get to <##>. By reporting a side effect, you can help provide more information on the safety of this medicine.

This information is not intended to take the place of discussions with your doctor or other healthcare professionals who are treating your relapsed/refractory Philadelphia chromosome negative acute lymphoblastic leukemia. Read the BLINCYTO patient leaflet provided to you by the doctors or nurses, as well as this educational brochure.

Version 1.0

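### The success statement calls for a majority who received the materials and know the messages, but the planned analysis yields only two separate summaries that cannot show it

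*Protocol*

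**What the plan says.** Sections 4 (Hypothesis/Estimation) and 8.2 carry the only benchmark in the Protocol. The survey will help indicate that the measures are successful "if a majority of patients and caregivers participating in the survey confirm receipt of the patient/caregiver brochure and card and have knowledge of" the key safety messages in the brochure. Section 8.2 then adds: "These results will be interpreted in context of the wider study including the secondary objectives and the results of individual questions, response rate and recruitment". Section 7.3 states: "This study is descriptive and therefore no formal hypothesis will be tested".

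Sections 9.3.2 and 9.7.2.4 fix the two primary endpoints one by one:

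- Receipt "will be assessed through the percentage of patients and caregivers who received the brochure and/or card".
- Knowledge is a mean of individual scores: "An individual patient/caregiver score is calculated as the proportion of all knowledge questions with correct responses".

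The opening of Section 9.7.2.4 promises, for patients and caregivers separately, the percentage with a positive response for each endpoint. It does not say what a positive response is for a knowledge score. The Full Analysis Set (Section 9.7.2.3.1) requires a completed, valid questionnaire, not receipt. Understanding is restricted to people who read the materials; knowledge has no such restriction. Section 9.7.2.5.1 plans results by whether the materials were read, and Section 9.9 calls subgroup analyses exploratory and limited.

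**The concern.** The benchmark and the analysis do not meet, in three respects.

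1. **Joint against separate.** The benchmark has one subject, a majority, and two things that this majority does. The analysis summarises each over everyone and never counts the people who do both.
2. **Receipt is defined in two ways.** The benchmark needs brochure and card. The endpoint is satisfied by either, so a person holding only the card counts as a recipient, although the knowledge endpoint concerns the brochure's content.
3. **A mean is not a majority.** Without an individual cut-off, a mean score does not say what share of people have knowledge.

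Knowledge of the messages also does not imply receipt of the patient brochure. Table 1 gives nurses a brochure with the same advice for patients: "Recommendation for patients not to drive while receiving Blincyto and to contact immediately the treating physician / nurse if they experience neurological symptoms". The patient brochure tells readers to "refer to the Patient Leaflet, provided with this brochure".

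What is at stake is the reading of the headline result. Section 9.1 presents the survey as early enough to correct the educational programme. If two separate figures above one half are taken as meeting the benchmark, a shortfall in people who were both reached and informed could go unnoticed.

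**Working it through.** The Protocol gives no figure to reproduce: the benchmark contains no number beyond a majority (taken here as more than 50%), and the sample sizes and confidence limits in Tables 2 and 3 are redacted.

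**Inputs**

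- R, the share who received the materials: 60% to 90%, the range used for receipt in Section 9.5.
- K, the share who have knowledge: assumed over the same range. The Protocol gives no value and no cut-off, so K is a yes/no simplification of the planned mean score.

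**Step 1: what two separate shares say about the joint share J**

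- Smallest possible J = max(0, R + K − 1).
- Largest possible J = min(R, K).
- If knowledge is independent of receipt, J = R × K.

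| R | K | Smallest J | J if independent | Largest J |
|---|---|---|---|---|
| 60% | 60% | 20% | 36% | 60% |
| 70% | 70% | 40% | 49% | 70% |
| 80% | 60% | 40% | 48% | 60% |
| 80% | 80% | 60% | 64% | 80% |
| 90% | 90% | 80% | 81% | 90% |

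A joint majority is certain only when R + K − 1 > 0.50, that is, R + K > 150%.

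**Step 2: the 60%/60% row as counts, for an assumed 50 respondents**

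Thirty received and thirty know.

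- Independence: 60% of 30 recipients = 18 do both; 18/50 = 36%.
- Lower extreme: all 20 non-recipients know, leaving 10 knowing recipients; 10/50 = 20%. Knowledge is then 10/30 = 33% in recipients and 20/20 = 100% in non-recipients.
- Joint majority: at least 26 people must do both, so 26/30 = 87% of recipients know and at most 4/20 = 20% of non-recipients do.

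At 60%/60%, the joint benchmark is therefore met only if knowledge is strongly concentrated in recipients. The two separate summaries cannot show whether it is.

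**Step 3: a mean score does not fix K**

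Section 9.5 puts the knowledge score on a scale from 0 to 10. Take a mean of 6 and, for illustration only, a cut-off of 7. If everyone scores 6, nobody has knowledge. If 60% score 10 and 40% score 0, the mean is again 6 and 60% have knowledge. The same mean fits either side of a majority.

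**The case against.** **This is not a decision rule.** Correct. The wording is that the survey will help indicate success, no hypothesis is tested, and other information is to be weighed. Probabilities of the benchmark being met by chance would treat it as a pass/fail test, and would need an unredacted sample size and a yes/no knowledge variable, neither of which the Protocol supplies. None is offered here. A benchmark read in context must still be computable from the planned output.

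**The sentence already means a joint majority.** It most naturally does. A reader might infer that the Protocol defines success as two separate majorities; the text does not say that. The fault is that Section 9.7.2.4 supplies nothing else to read the statement from.

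**The 20% figure is extreme.** It is: it needs recipients to know far less than non-recipients. If receipt and knowledge are not negatively associated, 60%/60% gives at least 36%, which is still a minority.

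**The read/not-read breakdown covers this.** In part, since someone who never received the materials would normally fall among the non-readers. That group also contains recipients who did not read, the breakdown is exploratory, and it does not give the joint share.

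**This belongs in the SAP.** A cross-tabulation alone would; Section 9.7 leaves table shells to the SAP, which is not at hand. The benchmark and endpoint definitions, however, are fixed in the Protocol and disagree there.

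**Other sources of knowledge.** The nurse brochure is itself one of the risk minimisation measures, and the leaflet comes with the patient brochure, so neither is wholly outside the programme. They show only that knowledge is no proxy for receipt of the patient brochure.

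**Conclusion.** The point holds as a mismatch between fixed parts of the Protocol. The success statement calls for a share of people that the specified endpoints cannot deliver, because receipt and knowledge are summarised apart, receipt is defined more loosely than in the statement, and individual knowledge is undefined. The consequence lies mainly in the lower part of the Protocol's own 60% to 90% receipt range: at 60% on both, the joint share is 36% under independence (bounds 20% to 60%), and at 70% on both it is 49% (40% to 70%). At 80% to 90% on both, the readings largely agree. These figures rest on an assumed K and a yes/no view of knowledge.

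A reader might go further and infer that the fault is a benchmark that credits a brochure with no effect, and that a joint criterion would cure this. The documents do not support that. With no effect, J = R × K still exceeds 50% once R and K are each above √0.5 = 70.7%. This is a limit of an uncontrolled survey, and the Protocol discloses it in Appendix B (comment to checklist Section 5): "No exposure-outcome association will be assessed".

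**What to change.** - **Sections 4 and 8.2:** state the criterion per person and separately for patients and caregivers: more than half both confirm receipt of brochure and card and have knowledge of the key messages.
- **Sections 9.3.2 and 9.7.2.4:** define, before data are seen, what counts as an individual having knowledge, and use the same receipt definition as the success statement. The mean score can stay as a summary.
- **Section 9.7.2.4:** add the receipt-by-knowledge cross-tabulation for each respondent group, with the joint percentage and its exact (Clopper-Pearson) 95% confidence interval as the figure from which the statement is read. Show knowledge by receipt status beside it, descriptively.
- **Conclusion wording:** limit it to reach of the materials and level of knowledge, not an effect of the brochure.

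The cost is a change of wording, one agreed cut-off and one table from data already collected. The joint percentage cannot exceed either separate percentage, so the headline will look less favourable. The non-recipient group may be too small to interpret: at 90% receipt and an assumed 30 respondents, it is 0.10 × 30 = 3 people.

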9.1 Study Design

To meet the study objectives, an observational cross-sectional survey of patients and caregivers is planned in **a selection of EU countries. Target countries may include France, Germany, Italy, Spain, the UK, and potentially other European countries.** , **The final list of countries will be dependent on country-specific factors including the timing of Blincyto launch and levels of usage .**

The **timing** of the patient/caregiver survey is sufficiently early in the product lifecycle to identify and promptly **rectify** any aspect of the educational program that might need to be modified.

9.2 Setting and Study Population

The survey will be conducted in **a selection of EU countries. Target countries may include France, Germany, Italy, Spain, the UK, , and potentially other European countries.** The selection of countries **will correspond** to the combination of expected product uptake and adequate timing of the product launch, **in order** to allow for the completion of the study within the required timeframe. **The choice of study countries will also attempt** to support the external validity of the study findings by collectively, **encompassing** a wide range of healthcare systems: the General Practitioner gate-keeper function, health insurance which is part of the social security system and mixed.

This rationale is based on factors that may change as the study progresses (i.e. initial usage forecasts and planned launch schedule). Therefore, if recruitment of patients and caregivers is slower than anticipated other countries may be added to meet sample size goals within the study timeline.

9.2.1 Study Period

Product launch is expected to occur in a staggered manner in Europe and the time needed for regulatory/ethics approvals varies between countries. **Therefore, the duration of the study period will vary between countries, and the entire study period will allow enough time for data collection for the later launching countries.**

As this is a one-wave cross-sectional design, data from patients and caregivers will be collected at one point in time.

9.2.2 Selection and Number of Sites

Site selection and sampling strategy:

The sampling frame will consist of haematology centres (and identified prescribers where available) where Blincyto is prescribed or expected to be prescribed after its launch in each participating country (data on file provided by Amgen). This list will be assembled by working closely with Amgen's country affiliates to identify Blincyto prescribers or potential prescribers. Given the poor prognosis of R/R ALL and the complexities of allogenic HSCT and experience required to manage these patients, and the highly selective use of Blincyto, usage is expected to be mainly in tertiary haematological centres.

CCI

As shown in [Figure 1](#), all centres in the list will be approached (by mail, telephone, fax or email, as appropriate) to identify prescribers or potential prescribers willing to participate. During this initial contact, site eligibility will be assessed to ensure that they meet the requirements to participate in the study: at least one staff hematologist with experience of managing patients with ALL; a staff member available to coordinate the research; the centre has already prescribed Blincyto to one patient or is likely to prescribe Blincyto to at least CCI patients **during the study period**. The number of eligible hematologists identified and contacted but not enrolled in the study, the number of non-respondents and the number eligible and willing to participate will be recorded.

[figure not shown]
In case the number of patients that each unit is able to recruit proves to be lower than expected, the inclusion of additional hospitals will be considered.

Patient/caregiver selection:

Haemato-oncologists/nurses in participating centres will include patients and their associated caregivers who fulfil all the selection criteria listed below in a consecutive manner according to the date of initiation of treatment with Blincyto until reaching the target number of patients/caregivers to be recruited per centre. Caregivers can be a spouse, family member, friend or professional helper who has helped with Blincyto treatment. The consecutive selection of patients and caregivers at each site is designed to minimise selection bias and to allow for the study results to be generalisable to the entire population of Blincyto treated patients. To assess generalizability of the data, sites will be asked to keep a log of anonymized demographic profiles (age and sex) of patients administered Blincyto, and their caregivers.

CCI

[figure not shown]
Figure 1. Illustration of sampling strategy

Patients/caregivers who agree to participate in the study with informed consent will be asked to complete a paper questionnaire after discharge from hospital **preferably** when they return to clinic for a bag change or monitoring (Figure 2). Both the patient and the caregiver will be invited to participate in the survey: **however, one can participate without the participation of the other**. If the patient is not well enough to complete the questionnaire on returning to clinic after hospital discharge on Blincyto, the patient will be asked again at the next visit. If a caregiver is not available at a visit, they will be asked at the next available visit to participate. Only one caregiver per patient will be recruited.

Appropriate measures will be adopted to ensure physicians do not influence patient/caregiver's choices (e.g. patients and caregivers will place their completed questionnaires in a sealed envelope).

Figure 2. Illustration of treatment characteristics and questionnaire administration

Note: Patients/Caregivers will complete the questionnaire based upon their first exposure to Blincyto at home. However, the questionnaire may be administered subsequent to blincyto cycle 1

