The information in this document cannot be used for any purpose other than the evaluation or conduct of the research without the prior written consent of Amgen Inc.

If you have questions regarding how this document may be used or shared, call CCI
Amgen's general number in the US ([name]).

Investigator's Agreement

I have read the attached protocol entitled 'A cross-sectional survey of patients and caregivers receiving Blincyto in routine clinical practice in Europe to evaluate the effectiveness of additional risk minimisation measures', dated 06 November 2016, and agree to abide by all provisions set forth therein.

I agree to ensure that the confidential information contained in this document will not be used for any purpose other than the evaluation or conduct of the clinical investigation without the prior written consent of Amgen Inc.

Signature

Name of Investigator

Date (DD Month YYYY)

Study Design Schema

Questionnaire development and testing

The patient/caregiver questionnaire will be developed in English. This questionnaire will be first reviewed by 5 haemato-oncology non-ALL patients not treated with Blincyto and caregivers in the UK and will be later translated and linguistically validated with 3 patients/caregivers in each of the participating countries.

Identify haematology centres where Blincyto is or may be prescribed

Amgen's country affiliates will work with CCI to identify centres where Blincyto is prescribed or may be prescribed. A sampling list will be created. All centres/identified haemato-oncologists in this list will be approached. A qualification assessment will be performed to identify those centres/haematologists who are eligible and willing to participate. A total of approximately 10 haematology centers will be selected to participate in the study

Selection of patients and caregivers

Patients and their caregivers will be selected by the centre's haemato-oncologists/nurses in a consecutive manner based on the date of initiation of treatment with Blincyto. Sites will be asked to keep a log of anonymized demographic profiles (age and sex) of all patients administered Blincyto and their caregivers.

Survey data collection

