9.7.2.1 General Considerations

Categorical data will be summarized by counts and percentages. Continuous data will be summarized using number, mean, standard deviation (SD), median, quartiles, minimum and maximum and in the case of non-normally distributed data, median, range and interquartile range. Corresponding 95% confidence intervals will be reported as appropriate. No adjustment will be made for multiple comparisons or for multiple analyses. All figures will be presented to three decimal places.

The statistical analysis will include a summary of the study conduct, a descriptive analysis and the analysis of the objectives. Site characteristics (type of centre i.e. academic/non-academic) will be described.

Patient/caregiver representativeness: Patients/caregivers approached at the sites for enrollment, whose demographic profile information has been collected in the patient log (age and gender), will be divided into:

- Eligible patients/caregivers who agree to participate in the study

- Eligible patients/caregivers who refuse to participate in the study

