9.9 Limitations of the Research Methods

The number of patients willing/able to participate in the survey may be lower than expected because of the severity of the condition and complications during **treatment with Blincyto**: neutropenic fever, infections, and neurological side effects. Responses by caregivers may be anticipated to be different (better?) than patients, as they are often more attentive of the details of the management of their family member or friend, especially in these patients, many of whom will experience side effects and be quite ill during their therapy with Blincyto. This will be assessed by analyzing patients and caregivers separately.

The questionnaire has been designed to facilitate completion by the patient/caregiver on paper. For this reason, some of the questions that address secondary endpoints refer to 'educational materials' in general (e.g. understanding, usage) and do not allow drawing conclusions for each type of material i.e. card and brochure. However, most of the questions apply only to the brochure and some of the questions apply only to the card.

The survey will exclude patients (caregivers of patients) who have only received Blincyto in hospital. This restriction will result in a more meaningful assessment as only patients/caregivers who have the chance to have used the materials will be included; materials are mainly used in the outpatient setting where MEs are more likely to occur. In

addition, the completion of the survey by the patient/caregiver will be restricted to the period after discharged from hospital and ambulatory treatment at home. This time interval is expected to allow sufficient time for the provision and usage of the materials, and the occurrence of MEs (if any), without hindering recruitment.

The survey may be affected by selection bias within centres and non-participation. Consecutive recruitment based on treatment initiation during the study period will be used to avoid selection bias. A log of patients initiating Blincyto during the study period will be kept to check this recruitment process.

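### Consecutive selection inside self-selected centres does not support generalising receipt to all Blincyto-treated patients, and the visible checks do not reach the centre level

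*Protocol*

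**What the plan says.** **Centre entry.** Under 9.2.2, "all centres in the list will be approached (by mail, telephone, fax or email, as appropriate) to identify prescribers or potential prescribers willing to participate". To qualify, a centre needs a haematologist experienced in ALL, "a staff member available to coordinate the research", and past or likely Blincyto prescribing. The Study Design Schema adds: "A total of approximately 10 haematology centers will be selected to participate in the study".

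**Centres that do not enrol.** 9.2.2 undertakes to record "The number of eligible hematologists identified and contacted but not enrolled in the study", and further that "the number of non-respondents and the number eligible and willing to participate will be recorded".

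**Generalisability.** The patient/caregiver part of 9.2.2 attributes two aims to consecutive selection at each site: to reduce selection bias, and "to allow for the study results to be generalisable to the entire population of Blincyto treated patients". The stated means of assessing this is a log, kept by the sites, of the age and sex of treated patients and their caregivers.

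**Planned checks.** The representativeness analysis in 9.7.2.1 takes eligible persons approached at the sites and divides them into those who agree and those who refuse. On centres it says: "Site characteristics (type of centre i.e. academic/non-academic) will be described". No comparator is named.

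**Limitations.** 9.9 states: "The survey may be affected by selection bias within centres and non-participation". The remedy offered there is consecutive recruitment, and the check is a log of patients starting treatment.

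**The concern.** There are two stages of selection: which centres join, and which persons within them take part. The protocol's claim covers the whole treated population, but its design feature and its visible checks address only the second stage.

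The first stage matters for receipt. The first research question in section 8 asks whether the safety information reached its audience, and receipt is a primary endpoint (9.3.2). Whether a patient receives the card and brochure plausibly depends on the centre. 9.9 itself accepts that centres may change how much information they give because a survey is running. A centre that is willing to be surveyed and has someone to coordinate research may differ in this from one that declines or does not reply. Age and sex are weak proxies for such a difference.

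At stake is the conclusion drawn from the receipt percentage. It would be read as describing all treated patients in Europe, although it is known only for those in about 10 volunteer centres.

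**Working it through.** **Step 1: what each element can detect.**

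| Element | Section | Acts on | Reaches centre selection? |
|---|---|---|---|
| Consecutive selection | 9.2.2, 9.9 | Persons in enrolled centres | No |
| Age and sex log | 9.2.2, 9.9 | Persons in enrolled centres | No |
| Agree versus refuse | 9.7.2.1 | Persons approached at the sites | No |
| Site type described | 9.7.2.1 | No comparison group stated | Not as stated |
| Numbers contacted, not enrolled, not responding | 9.2.2 | Haematologists and non-respondents | Shows uptake, not differences |

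Nothing visible links the centres that joined to those that did not, other than numbers.

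**Step 2: how the error depends on unknowns.** Let f be the share of Blincyto patients treated in participating centres, Rp receipt in those centres and Rn receipt in the others.

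Receipt in all treated patients = f × Rp + (1 − f) × Rn

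Error of the survey figure = Rp − [f × Rp + (1 − f) × Rn] = (1 − f) × (Rp − Rn)

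The protocol gives none of f, Rp or Rn, so no stated figure can be reproduced. The values below are assumptions that show sensitivity; they are not estimates. Error in percentage points:

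| f | gap 10 | gap 20 | gap 30 | gap 40 |
|---|---|---|---|---|
| 0.2 | 8 | 16 | 24 | 32 |
| 0.4 | 6 | 12 | 18 | 24 |
| 0.6 | 4 | 8 | 12 | 16 |
| 0.8 | 2 | 4 | 6 | 8 |

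For example, f = 0.2 and a gap of 40 points give 0.8 × 40 = 32. If the other centres delivered better, the sign would reverse.

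**Step 3: when the reading would change.** Section 8.2 reads success from a majority of participants confirming receipt. Taking a majority as more than 50% (my reading), the gap that brings the all-patient value down to 50% is (Rp − 0.50)/(1 − f).

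- Rp = 60%, the lowest value shown in Table 2: 0.10/0.8 = 12.5 points at f = 0.2; 0.10/0.6 = 16.7 at f = 0.4; 0.10/0.4 = 25 at f = 0.6; 0.10/0.2 = 50 at f = 0.8.
- Rp = 80%: 0.30/0.8 = 37.5 points at f = 0.2; 0.30/0.6 = 50 at f = 0.4; 0.30/0.4 = 75 at f = 0.6. At f = 0.8 the formula gives 150 points, which is impossible.

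The reading is therefore sensitive when observed receipt is near 60% and coverage is low, and robust when both are high.

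**Step 4: does the interval cover it?** No. The sample size is blacked out. For an assumed n of 50 with 80% observed, the exact Clopper-Pearson interval is 66.3% to 90.0%, whatever receipt is in the other centres.

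**The case against.** A reader might infer that non-participating centres are only counted and never compared. The visible text does not establish that. Text is blacked out next to both the sampling description and the generalisability sentence, and Figure 1 is not shown. 9.4 and 9.6.2 provide for a database of the feasibility and recruitment process whose fields are not stated. 9.7.2.3.1 plans a description of the populations identified during recruitment. The recorded numbers begin with haematologists, not centres, and country is known because the list is built per participating country. This objection stands: one can say only what the visible text commits to.

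A reader might also infer that receipt will be overstated, and unnoticed. The documents show neither. There are no data that volunteer centres deliver the materials better. Section 7.1 obliges the marketing authorisation holder to provide the materials in every member state where the product is marketed, and 9.2.2 expects use mainly in tertiary centres, which may limit differences. Section 8.2 reads the results alongside response rate and recruitment, and 9.9 names non-participation, so low uptake would be visible. This stands too, although uptake alone does not show whether or how the centres differ.

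Finally, the layout of tables belongs to the statistical analysis plan. That is fair for the shell. It does not excuse the sentence in 9.2.2, which claims more than the design can give. A later plan can tabulate only what was kept when centres were contacted, and the protocol does not say that centre characteristics will be kept.

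**Conclusion.** The point holds as one about the claim and its checks. The protocol rests generalisability to the whole treated population on a within-centre device, while centres enter by willingness and resources. The visible checks stop at the door of the enrolled centre. The design does not support the stated generalisability for receipt.

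The size and direction of any bias are unknown. The 2 to 32 points above rest wholly on assumed coverage of 20% to 80% and assumed gaps of 10 to 40 points; no figure in the protocol supports a particular cell. That receipt varies by centre is plausible but not documented.

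The change is worth making because it alters what may be concluded from a primary endpoint and costs little. It is not evidence that the receipt result will be wrong.

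**What to change.** 1. In 9.2.2, limit the generalisability statement to patients and caregivers in participating centres, unless the centre comparison in item 3 supports more. In 9.9, name selection at centre level as a limitation distinct from selection within centres.
2. In the recruitment database already planned, keep country and academic or non-academic type for every listed centre. For centres that answer the initial contact, also keep the actual or expected number of Blincyto patients.
3. In 9.7.2.1, add one table comparing participating, eligible-but-not-enrolled and non-responding centres on these characteristics, with patient numbers shown only where a centre answered.

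The cost is a few extra columns, one table and a more modest claim, with no added burden on patients or caregivers. The table shows whether centres differ on these characteristics. It does not measure receipt in centres that did not take part, so item 1 is needed whatever the table shows.
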